1. PRE-INJECTION PROCEDURES

The following procedures will be used to minimize the risk of potential adverse events associated with intravitreal (IVT) injections (e.g., endophthalmitis).

Aseptic technique will be observed by clinic staff involved in the administration tray assembly, anesthetic preparation, and study treatment preparation and administration. In addition to the procedures outlined below, any additional safety measures in adherence to specific institutional policies associated with IVT injections will be observed.

The above procedures (except where noted) will be conducted by the physician performing the IVT administration of study treatment. At the discretion of the Investigator, patients may self-administer ophthalmic broad-spectrum antimicrobial drops on days prior to study treatment administration.

At the discretion of the Investigator, the sites may use either ophthalmic drops or lidocaine injection for study eye anesthesia.

2. PROCEDURE FOR PROPACAINE- OR TETRACAINE-BASED ANESTHESIA

If using propacaine- or tetracaine-based ophthalmic drops for anesthesia, the treatment administrator physician or technician (if applicable) assembles the supplies and prepares a sterile field. Supplies include 10% povidone iodine swabs, sterile surgical gloves, 4 × 4 sterile pads, a pack of sterile cotton-tipped applicators, eyelid speculum, sterile ophthalmic drape, 5% povidone iodine ophthalmic solution, ophthalmic broad-spectrum antimicrobial solution (e.g., ofloxacin ophthalmic solution, trimethoprim-polymyxin B ophthalmic solution, moxifloxacin ophthalmic solution, or gatifloxacin ophthalmic solution single-use vial), and treatment administration supplies.

- Instill two drops proparacaine- or tetracaine-based ophthalmic drops into the study eye, followed, at the discretion of the Investigator, by two drops of ophthalmic antimicrobial solution.
- Wait 90 seconds.
- Instill two more drops of proparacaine- or tetracaine-based ophthalmic drops into the study eye,

Appendix 4

Study Treatment Administration Procedure (cont.)

- Disinfect the periocular skin and eyelid of the study eye in preparation for study treatment administration. Scrub the eyelid, lashes, and periorbital skin with 10% povidone iodine swabs, starting with the eyelid and lashes and continuing with the surrounding periocular skin. Ensure that the eyelid margins and lashes are swabbed, and proceed in a systematic fashion, from medial to temporal aspects.
- The treatment administrator physician will glove, place sterile ophthalmic drape to isolate the field, and place the speculum underneath the eyelid of the study eye.
- Instill two drops of 5% povidone iodine ophthalmic solution in the study eye, ensuring that the drops cover the planned injection site on the conjunctiva.
- Wait 90 seconds.
- Saturate a sterile, cotton-tipped applicator with proparacaine- or tetracaine-based drops and hold the swab against the planned IVT injection site for 10 seconds.
- Use a sterile 4 × 4 pad in a single wipe to absorb excess liquid and to dry the periocular skin.
- Instruct patient to direct gaze away from syringe prior to study treatment administration.

3. PROCEDURE FOR LIDOCAINE INJECTION-BASED ANESTHESIA

If using lidocaine injection for anesthesia, treatment administrator physician or technician (if applicable) assembles the supplies and prepares a sterile field. Supplies include 10% povidone iodine swabs, sterile surgical gloves, 4 × 4 sterile pads, a pack of sterile cotton-tipped applicators, eyelid speculum, sterile ophthalmic drape, 0.5% proparacaine hydrochloride, 5% povidone iodine ophthalmic solution, 1% lidocaine for injection, ophthalmic antimicrobial solution, and treatment administration supplies.

- Instill two drops of 0.5% proparacaine hydrochloride into the study eye, followed, at the discretion of the Investigator, by two drops of broad-spectrum antimicrobial solution (e.g., ofloxacin ophthalmic solution, trimethoprim-polymyxin B ophthalmic solution, moxifloxacin ophthalmic solution, or gatifloxacin ophthalmic solution single-use vial).
- Disinfect the periocular skin and eyelid of the study eye in preparation for injection. Scrub the eyelid, lashes, and periorbital skin with 10% povidone iodine swabs, starting with the eyelid and lashes and continuing with the surrounding periocular skin. Ensure that the eyelid margins and lashes are swabbed, and proceed in a systematic fashion, from medial to temporal aspects.
- The treatment administrator physician will glove, place sterile ophthalmic drape to isolate the field, and place the speculum underneath the eyelid of the study eye.
- Instill two drops of 5% povidone iodine ophthalmic solution in the study eye, ensuring that the drops cover the planned injection site on the conjunctiva.
- Wait 90 seconds.

Appendix 4

Study Treatment Administration Procedure (cont.)

- Saturate a sterile, cotton-tipped applicator with 0.5% proparacaine hydrochloride drops and hold the swab against the planned IVT injection site for 10 seconds in preparation for the subconjunctival injection of 1% lidocaine hydrochloride ophthalmic solution for injection (without epinephrine).
- Inject 1% lidocaine (without epinephrine) subconjunctivally.
- Use a sterile 4 × 4 pad in a single wipe to absorb excess liquid and to dry the periocular skin.
- Instruct patient to direct gaze away from syringe prior to study treatment administration.

4. PROCEDURE FOR LIDOCAINE-GEL BASED ANESTHESIA

If using lidocaine-gel for anesthesia, the treatment administrator physician or technician (if applicable) assembles the supplies and prepares a sterile field. Supplies include 10% povidone iodine swabs, sterile surgical gloves, 4 × 4 sterile pads, a pack of sterile cotton-tipped applicators, eyelid speculum, sterile ophthalmic drape, 5% povidone iodine ophthalmic solution, ophthalmic broad-spectrum antimicrobial solution (e.g., ofloxacin ophthalmic solution, trimethoprim-polymyxin B ophthalmic solution, moxifloxacin ophthalmic solution, or gatifloxacin ophthalmic solution single-use vial), and treatment administration supplies.

- Instill two drops of 5% povidone iodine ophthalmic solution in the study eye, followed at the discretion of the investigator, by two drops of ophthalmic antimicrobial solution.
- Wait 90 seconds
- Instill lidocaine gel onto the planned injection site in the study eye
- Wait 3 minutes
- Instill lidocaine gel onto the planned injection site in the study eye
- Disinfect the periocular skin and eyelid of the study eye in preparation for study treatment administration. Scrub the eyelid, lashes, and periorbital skin with 10% povidone iodine swabs, starting with the eyelid and lashes and continuing with the surrounding periocular skin. Ensure that the eyelid margins and lashes are swabbed, and proceed in a systematic fashion, from medial to temporal aspects
- The treatment administrator physician will glove, place sterile ophthalmic drape to isolate the field, and place the speculum underneath the eyelid of the study eye.
- Instill two drops of 5% povidone iodine ophthalmic solution in the study eye, ensuring that the drops cover the planned injection site on the conjunctiva
- Wait 90 seconds
- Saturate a sterile, cotton-tipped applicator with proparacaine- or tetracaine-based drops and hold the swab against the planned IVT injection site for 10 seconds

Appendix 4

Study Treatment Administration Procedure (cont.)

- Use a sterile 4 × 4 pad in a single wipe to absorb excess liquid and to dry the periocular skin
- Instruct patient to direct gaze away from syringe prior to study treatment administration

5. INTRAVITREAL ADMINISTRATION OF STUDY TREATMENT

Study treatment must be prepared according to the detailed instructions in the Pharmacy Manual. The instructions in the Pharmacy Manual cover all steps until the syringe is ready for treatment administration.

After preparing the study eye as outlined above:

- For RO6867461 or administration: insert the syringe through an area 3.0 to 4.0 mm posterior to the limbus (aphakic/pseudophakic patients 3.0-3.5 mm), avoiding the horizontal meridian, and aiming toward the center of the globe. The injection volume should be delivered slowly. The needle should then be removed slowly to ensure that all drug solution is in the eye. Refer to Section 6 for detailed post-injection procedures.
- For sham administration: the patients do not receive an actual injection. The treatment administrator physician will withdraw the tuberculin syringe plunger to the 0.1 mL mark on the syringe, then place the hub of the syringe (without the needle) against the pre-anesthetized conjunctival surface. The treatment administrator physician will then press the syringe hub firmly against the globe and then slowly depress the plunger, mimicking the action of an injection.

The injection site should be rotated at every study treatment visit.

6. POST-INJECTION PROCEDURES

At the discretion of the Investigator, drops of ophthalmic antimicrobial drops could be instilled in the study eye after study treatment administration and for the days following study treatment administration.

Discard all administration materials (i.e., syringe, needles) in the sharps container.

## 1. BACKGROUND

This Statistical Analysis Plan (SAP) documents the statistical methods for summarizing and analyzing the efficacy and safety data from study BP29647. The main purpose of this SAP is to describe the data handling rules, derivation rules, and statistical analysis methods.

[figure not shown]
## 2. STUDY DESIGN

This is a multiple-center, multiple-dose and regimen, randomized, active comparator controlled, double-masked, five parallel groups, 36-week study in patients with subfoveal CNV secondary to AMD. The study design is shown in Figure 1 Study Design.

The five groups of this study are as follows.

- Arm A: 0.5 mg ranibizumab IVT every 4 weeks for 32 weeks (9 injections)
- Arm B: 1.5 mg RO6867461 IVT every 4 weeks for 32 weeks (9 injections)
- Arm C: 6 mg RO6867461 IVT every 4 weeks for 32 weeks (9 injections)
- Arm D: 6 mg RO6867461 IVT every 4 weeks up to Week 12 (4 injections), followed by 6 mg RO6867461 IVT every 8 weeks (i.e., on Weeks 20 and 28; 2 injections)
- Arm E: 0.5 mg ranibizumab IVT every 4 weeks up to Week 8 (3 injections), followed by 6 mg RO6867461 IVT every 4 weeks (6 injections)

**Figure 1 Study Design**

These treatment arms have been chosen to compare the treatments in a treatment-naïve population and in an anti-VEGF-incomplete-responder population. For the treatment-naïve population the arms B and C will be compared with the reference arm A. For the anti-VEGF incomplete responder population, a subgroup of arm E will be compared to a similar subgroup of arm A.

## **2.1 PROTOCOL SYNOPSIS**

The Protocol Synopsis is in Appendix 1. For additional details, see the Schedule of Assessments in [Appendix 2](#).

## **2.2 OUTCOME MEASURES**

For efficacy analyses only measurements in the study eye are used; except where explicitly stated.

For safety analyses events and measurements in both eyes will be included in the analyses, except for imaging.

### **2.2.1 Primary Efficacy Outcome Measures**

The primary efficacy outcome measure is the mean change from baseline in BCVA at Week 36 using the ETDRS modified charts.

### **2.2.2 Secondary Efficacy Outcome Measures**

The secondary efficacy outcome measures include functional (BCVA) and anatomical PD imaging measures relevant to the mechanism of action of RO6867461 as follows.

BCVA:

- Proportion of patients gaining  $\geq 15$  letters from baseline in BCVA at Week 36
- Proportion of patients with BCVA of 20/40 or better at Week 36
- Proportion of patients with BCVA of 20/200 or worse at Week 36

Anatomic outcome measures by SD-OCT:

- Mean change from baseline in foveal center point thickness at Week 36
- Mean change from baseline in mean CST (1 mm diameter) at Week 36
- Proportion of patients with no intraretinal fluid, subretinal fluid, cysts, or pigment epithelial detachment at Week 36 (dry retina definition No1)

Anatomic outcome measures by FFA:

- Mean change from baseline in total area of CNV at Week 36
- Mean change from baseline in total area of CNV component at Week 36
- Mean change from baseline in total area of leakage at Week 36

### **2.2.3 Exploratory Efficacy Outcome Measures**

The exploratory outcome measures for this study are the following:

- Proportion of patients gaining 5 or more, 10 or more, and 30 or more letters in BCVA on ETDRS charts over time
- Proportion of patients losing 5 or more, 10 or more, 15 or more, and 30 or more letters in BCVA on ETDRS charts over time

RO6867461—F. Hoffmann-La Roche Ltd  
Statistical Analysis Plan BP29647

- Proportion of patients with resolution of RAP and PCV (ICGA) over time

Combined dry retina outcome measures:

- Proportion of patients with absence of IRF, SRF and cysts – all by SD-OCT, and leakage by FFA at Weeks 12, 24 and 36 (dry retina definition No2)
- Proportion of patients with absence of IRF, SRF, cysts and PED - all by SD-OCT at Weeks 12, 24 and 36 (dry retina definition No3)

Individual dry retina outcome measures:

- Proportion of patients with absence of IRF (by SD-OCT) over time
- Proportion of patients with absence of SRF (by SD-OCT) over time
- Proportion of patients with absence of cysts (by SD-OCT) over time
- Proportion of patients with absence of PED (by SD-OCT) over time
- Proportion of patients with absence of leakage (by FFA) over time

**Table 1 Description of Secondary Outcome Measures**

Secondary Endpoint	Detailed Definition	Variable names used by central reading center (and combinations therefore for certain endpoints)
foveal center point thickness	Thickness from Inner Limiting Membrane to the Retinal Pigment Epithelial at the horizontal slice closest to the center of the fovea	OCTcentralretinalthickness (SDTM variables : CENT RET THICK R1-3)
mean CST	Mean thickness from Inner Limiting Membrane to the Retinal Pigment Epithelial over the 1 mm central subfield	OCTCentralSubfieldThickness (SDTM variables: CENT SUBFIELD THICK ILM-RPE R1-3)
intra-retinal fluid (IRF)	Presence of fluid within the retina	OCTIntraRetinalFluid (SDTM variable: INTRARETINAL FLUID)
cysts	Presence of cystoid space (fluid) in the retina	OCTCystoidSpaces (SDTM variable: CYSTOID SPACES)
sub-retinal fluid (SRF)	Presence of fluid between the retina and the retinal pigment epithelium	OCTSubretinalFluidThicknessNotPresent (derived from SDTM variable: Subret Fluid Thick)
pigment epithelial detachment (PED)	Presence of a detachment of the pigment epithelium from the Bruch's membrane  Dry retina Definition 1:	OCTPigmentEpithelialDefectThickness (SDTM variables: PED THICK R1-3)
area of CNV	Total area of CNV lesion	FATotalLesionSizeMM (SDTM variables: FA TOTAL LESION SIZE R1-3)
area of CNV component	Total area of CVN membrane	FAArea (SDTM variable: FA CNV SIZE R1-3)
total area of	Total area of fluorescein	FALeakage (SDTM variable: FA

RO6867461—F. Hoffmann-La Roche Ltd  
Statistical Analysis Plan BP29647

leakage	leakage	LEAKAGE R1-3)
---------	---------	---------------

- Biomarkers in plasma related to angiogenesis and inflammation: Ang-1, Tie-2, VEGFR, PLGF, bFGF, PDGF, IL-1b, IL-6, eotaxin, autotaxin
- Pro-angiogenic factors in aqueous humor and vitreous samples for patients who provide additional consent to participate.

#### **2.2.4 Pharmacokinetic Efficacy Outcome Measures**

The pharmacokinetic (PK) outcome measures for this study are as follows:

- PK profiles and parameters derived from the nonlinear mixed effects modeling approach following IVT administration of RO6867461, including the following parameters:

Primary parameters: CL and V

Secondary parameters:  $C_{max}$ ,  $AUC_{inf}$ ,  $AUC_{0-t}$ ,  $t_{max}$ ,  $t_{1/2}$

Compartmental analysis to assess IVT concentrations, as appropriate (exploratory)

RO6867461 concentrations in aqueous humor samples for patients who provide additional consent to participate (exploratory)

#### **2.2.5 Pharmacodynamic Biomarker Outcome Measures**

Plasma biomarker outcome measures for this study are as follows:

- Change in plasma levels of VEGF and Ang-2

#### **2.2.6 Safety Outcome Measures**

The safety outcome measures for this study are as follows:

- Incidence and severity of ocular adverse events
- Incidence and severity of non-ocular adverse events
- Incidence of laboratory abnormalities, based on hematology, clinical chemistry, and urinalysis test results
- Incidence of anti-RO6867461 antibodies
- ECGs
- Vital signs
- Other safety biomarkers

### **2.3 DETERMINATION OF SAMPLE SIZE**

#### **2.3.1 Sample Size and Power for Treatment-Naive Population Evaluation**

The sample size for the treatment-naive population is based on the primary efficacy outcome of mean change in BCVA from baseline to Week 36. Each RO6867461 dose or dose regimen group (Arms B, C, and D) will be compared to the control group (Arm A).

Consider 68 patients randomized to Arm A and 45 randomized to each of Arms B, C, and D, with a drop-out rate of 10%. Assuming a standard deviation of 13.5 letters, this sample size would provide approximately 80% power to detect a true difference of 5.9 letters at the one-sided  $\alpha$  level of 10%. The minimum detectable difference would be approximately 3.5 letters.

### **2.3.2 Sample Size and Power for anti-VEGF-Incomplete-Responder Population Evaluation**

The sample size for anti-VEGF–incomplete-responder population is based on the primary efficacy outcome of mean change in BCVA from Week 12 to Week 36 in the subset of anti-VEGF–incomplete-responders, between Arm A and Arm E.

Consider 68 patients randomized to both Arms A and E with 65% meeting the criteria for inclusion in anti-VEGF–incomplete-responder subgroup and a drop-out rate of 10%. Assuming a standard deviation of 9.7 letters, this sample size would provide approximately 80% power to detect a true different of 4.7 letters at the one-sided  $\alpha$  level of 10%. The minimum detectable difference would be approximately 2.7 letters.

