6.1.2 Sample Size and Power for Anti-VEGF-Incomplete-Responder Population Evaluation

The sample size for anti-VEGF–incomplete-responder population is based on the primary efficacy outcome of mean change in BCVA from Week 12 to Week 36 in the subset of anti-VEGF–incomplete-responders, between Arm A and Arm E.

Consider 68 patients randomized to both Arms A and E with 65% meeting the criteria for inclusion in anti-VEGF–incomplete-responder subgroup and a drop-out rate of 10%. Assuming a standard deviation of 9.7 letters, this sample size would provide approximately 80% power to detect a true different of 4.8 letters at the one-sided α level of 10%. The minimum detectable difference would be approximately 2.8 letters. If only 50% meet the criteria for inclusion in anti-VEGF–incomplete-responder subgroup, this sample size would provide approximately 80% power to detect a true different of 5.4 letters at the one-sided α level of 10%. The minimum detectable difference would be approximately 3.3 letters.

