#### **4.1.1.3 Population C: Anti-VEGF-Incomplete Responder Population**

The primary anti-VEGF-incomplete responder population is defined as sub-population of population B consisting of

- Population C: Patients in population B with BCVA  $\leq$  68 at Week 12 with at least one letter improvement relative to baseline.

Additional exploratory anti-VEGF-incomplete responder populations are defined as

- Population C1: Patients in population B with improvement of less than 15 letters at Week 12
- Population C2: Patients in population B without dry retina at Week 12 (dry retina definition No 2)

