#### **4.4.2 Baseline**

For the evaluation in the treatment-naïve population, the baseline measurement is the latest non-missing observation before the first dose of study medication. For the evaluation in the anti-VEGF–incomplete-responder population, the baseline is the observation from Study Week 12. If the week 12 observation is missing, the patient will not be included in the incomplete responder population. For patients who did not receive any study medication, baseline will be set as the last available assessment before and including day 1.

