#### **4.5.1.2 Evaluation in the anti-VEGF Incomplete Responder Population C**

For the evaluation of efficacy in the anti-VEGF–incomplete-responder all patients in the population C will be used.

The primary efficacy variable is BCVA change from Week 12 to Week 36. The primary efficacy analysis will be performed using a MMRM model described in section 4.5.1.1.

The model-based estimate of the difference in change from baseline between the treatment group (Arm E) and the control group (Arm A) means at Week 36, together with 95% Confidence and corresponding p-value will be reported as the primary efficacy measure in this population.

The mean and 95% confidence intervals within each treatment group and for the difference between RO6867461 treatment group and the control group change from baseline at the other time points will also be reported. There will be no formal correction for multiple comparisons.

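### The incomplete-responder power statement uses a 65% share set for Week 12 BCVA of 68 letters or fewer, but the SAP analyses the narrower Population C, and the stated 2.7 letters should be about 2.8

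*SAP*

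**What the plan says.** SAP 2.3.2 bases the incomplete-responder comparison on "68 patients randomized to both Arms A and E with 65% meeting the criteria for inclusion", with 10% drop-out, an SD of 9.7 letters and a one-sided 10% level. It states about 80% power for 4.7 letters and adds: "The minimum detectable difference would be approximately 2.7 letters". The protocol synopsis, and its copy in SAP Appendix 1, give the same pair.

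Protocol 6.1.2 uses identical inputs but prints "80% power to detect a true different of 4.8 letters" with a minimum detectable difference of about 2.8. It also gives a 50% scenario, which SAP 2.3.2 omits: "80% power to detect a true different of 5.4 letters" and "The minimum detectable difference would be approximately 3.3 letters".

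In protocol 3.2 and 6.6.1.2 the subgroup has one criterion, a Week 12 BCVA of 68 letters or fewer. SAP 4.1.1.3 defines Population C by a BCVA of at most "68 at Week 12 with at least one letter improvement relative to baseline". For the primary analysis, SAP 4.5.1.2 says "all patients in the population C will be used".

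SAP 4.4.2 says that for this evaluation "the baseline is the observation from Study Week 12". Under that baseline nobody could show a gain at Week 12, so baseline in the Population C definition is read here as Day 1.

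**The concern.** The SAP narrowed the group for a primary comparison but kept the power input for the wider one. Population C is a subset of the group to which the 65% refers, and no share is given for it, so the printed power does not describe the patients who will be analysed.

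The one-letter condition has a definite effect. A patient with 69 to 73 letters on Day 1 needs at least 70 at Week 12 to gain one, and so cannot also be at 68 or below. That whole randomization stratum is outside Population C.

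Protocol 3.1.2 allows an optional check of the subgroup share, with recruitment rising to at most 343 to reach about 80 subgroup completers. It refers to the criterion in protocol 3.2, which has no improvement condition. As the protocol is written, the target could look met while Population C falls short.

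Finally, the sample-size passages print two different pairs on the same inputs, and one printed value cannot be obtained from them.

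**Working it through.** **Inputs.** 68 randomized per arm, 65% share, 10% drop-out, SD 9.7 and one-sided 10% (SAP 2.3.2); 50% share (protocol 6.1.2); cap of 40% on Day 1 BCVA of 69 to 73 letters (protocol 4.2.1); stratification at 69 letters (protocol 4.3.1).

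**Formulas (normal approximation).** With n completers per arm:
- n = 68 × share × 0.9
- SE = 9.7 × √(2/n)
- power for 4.7 letters = Φ(4.7/SE − 1.2816)
- difference with 80% power = (1.2816 + 0.8416) × SE
- minimum detectable difference = 1.2816 × SE, the smallest observed difference that is significant. The same formula gives 13.5 × √(1/61.2 + 1/40.5) × 1.2816 = 3.50 for the treatment-naive comparison, matching the printed 3.5.

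**The plan's own figures at 65%.** n = 68 × 0.65 × 0.9 = 39.78 and SE = 2.175.
- Power = Φ(4.7/2.175 − 1.2816) = 81.0%. With 39 whole completers and the noncentral t it is 80.1%. The stated 80% reproduces.
- Difference with 80% power = 2.1232 × 2.175 = 4.62 (4.69 with n = 39 and t), consistent with 4.7.
- Minimum detectable difference = 1.2816 × 2.175 = 2.79 (2.84 with n = 39 and t). A value of 2.7 needs 2 × (9.7 × 1.2816/2.7)² = 42.4 per arm, and even a value rounding to 2.7 needs at least 40.87 (z) or 41.54 (t).

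**The protocol 6.1.2 pairs.**
- For 4.8 letters, power is 81.4% (n = 39, t) to 82.1% (n = 40, t), and the minimum detectable difference is 2.84 to 2.80.
- In the 50% scenario, n = 30 gives 80.5% power for 5.4 letters and a minimum detectable difference of 3.25.

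**Population C.** If the 40% cap is filled, stratification spreads that stratum about evenly over the arms, so the share is at most about 60%. In the table, the first figure uses unrounded n and z; the second uses whole completers and t.

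| Share | Status | n per arm | Power for 4.7 | Difference with 80% power | Minimum detectable difference |
|---|---|---|---|---|---|
| 65% | upper limit | 39.78 / 39 | 81.0% / 80.1% | 4.62 / 4.69 | 2.79 / 2.84 |
| 60% | ceiling if cap is filled | 36.72 / 36 | 78.7% / 77.7% | 4.81 / 4.88 | 2.90 / 2.96 |
| 50% | protocol's scenario, assumed for Population C | 30.6 / 30 | 73.0% / 72.0% | 5.27 / 5.36 | 3.18 / 3.25 |

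Power falls below 80% once the share is under about 63%.

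**Optional share check.** A 65% share on the protocol criterion projects 136 × 0.65 × 0.9 = 79.6 completers, so the target of about 80 looks met. At 60%, Population C would have 136 × 0.60 × 0.9 = 73.4. At 343 patients, Arms A and E together hold 343 × 6/12 = 171.5, and 80 completers need a share of 80/(171.5 × 0.9) = 51.8%.

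**The case against.** The strongest reply is that nothing material is wrong. The 80% is correct on its inputs. The 60% ceiling holds only if a maximum is reached, and 78% is close to a figure introduced as approximate. Protocol 6.1.2 already covers a 50% share, and recruitment may rise to 343, which would give about 85% power at a 60% share and 79% at 50%. The SD of the change in Population C is unknown in either direction: with 36 completers, an SD of about 9.34 instead of 9.7 restores 80%. The planned MMRM uses partial data and adjusts for covariates, so completer-based figures are only approximate.

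Most of this stands and limits the point to a small, conditional loss. It does not remove the mismatch. The SAP leaves out the 50% scenario, the extension is optional and tied in the protocol to the wider criterion, and no passage gives a share for the group analysed.

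A reader might also infer three stronger things that the documents do not support:
- That the printed pairs cannot come from any one sample size. That holds only if power is forced to exactly 80%. The 4.8 and 2.8 of protocol 6.1.2 fit its inputs at 81 to 82% power, and the 50% pair is within rounding.
- That the comparison is seriously underpowered. Shares below 60% have no source for Population C.
- That the share check will count the wrong patients. Its details are in the IMC agreement, which was not available.

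**Conclusion.** The power statement in SAP 2.3.2 is right for a Week 12 BCVA of 68 letters or fewer, but it is not a statement about Population C, the primary analysis set. The share of Population C is at most 65% on the plan's assumption and at most about 60% if the Day 1 cap is filled. At 60%, power for 4.7 letters is about 78% instead of 80%, and the difference with 80% power is about 4.8 to 4.9 letters. This rests on 68 per arm, 10% drop-out, one-sided 10%, completers only, and an SD of 9.7 carried over as an assumption.

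The minimum detectable difference of 2.7 in SAP 2.3.2 and both copies of the synopsis is a small error; the inputs give about 2.8. The 4.8 and 2.8 in protocol 6.1.2 are defensible alone but disagree with the other passages. These are worth correcting because they are stated figures for a primary comparison, not because the design fails.

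**What to change.** (a) In SAP 2.3.2, state that 65% refers to a Week 12 BCVA of 68 letters or fewer and that Population C is a subset of unknown share. Give figures for Population C at the 65% upper limit, the conditional 60% ceiling and the protocol's 50% scenario: power for 4.7 letters about 80/78/72%; difference with 80% power about 4.7/4.9/5.4 letters; minimum detectable difference about 2.8/3.0/3.2 letters. Label them approximate, with SD 9.7 assumed.

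(b) Align SAP 2.3.2, protocol 6.1.2 and both copies of the synopsis on about 4.7 and 2.8 letters at a 65% share. The protocol's 50% pair needs no correction.

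(c) If Population C stays the primary set, align the criterion in protocol 3.2 and 6.6.1.2 with SAP 4.1.1.3, naming Day 1 as the reference for the gain. The optional check in protocol 3.1.2 and the IMC agreement would then count Population C within the existing maximum of 343.

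Items (a) and (b) cost a few sentences and a short table, and the stated figures become slightly less favourable. Item (c) needs a protocol edit and a matching check of the IMC agreement. Its downside is that the permitted extension, up to 343 − 271 = 72 more patients, may be triggered more often. The SAP's analysis model does not change.
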